6.3 Exclusion criteria

Changes to exclusion criteria number 30:

For Sweden only: ~~Oral (except low-dose gestagen [lynestrenol and norethisteron]), injectable, or implanted hormonal contraceptives, intrauterine device, intrauterine system (for example, progestin-releasing coil), vasectomized male (with appropriate postvasectomy documentation of the absence of sperm in the ejaculate). Use of contraception is not required for female subjects who have not yet made their sexual debut and/or are not sexually active. Only highly effective methods of birth control are accepted (i.e. one that results in less than 1% per year failure rate when used consistently and correctly, such as implants, injectables, combined (estrogen and progestogen containing) oral/intravaginal/transdermal contraceptives, progestogen-only oral/injectable/implantable contraceptives, intrauterine device (IUD, IUS), sexual abstinence or vasectomised partner.~~

Protocol Amendment
Trial ID: NN8022-4180
UTN:U1111-1162-7101
EudraCT No.:2014-004353-14

~~CONFIDENTIAL~~

Date:
Version:
Status:
Page:

02 September 2016
1.0
Final
1 of 4

Novo Nordisk

**Protocol Amendment
no 2
to Protocol, final version 1.0
dated 01 June 2016**

Trial ID:NN8022-4180

**Effect of liraglutide for weight management in pubertal
adolescent subjects with obesity**

56-week, double-blind, randomised, parallel-group, placebo-controlled
multi-national trial followed by a 26-week period off study-drug

Trial phase: 3a

Applicable to Mexico

Amendment originator:

This ~~confidential~~ document is the property of Novo Nordisk. ~~No unpublished information contained herein may be disclosed without prior written approval from Novo Nordisk. Access to this document must be restricted to relevant parties.~~

Table of Contents

	Page
Table of Contents.....	2
1 Introduction including rationale for the protocol amendment	3
2 Changes	3
2.1 Section 1.0 Summary	3
2.2 Section 5.1 Type of Trial	4
2.3 Section 6.2 Inclusion criteria:	4
2.4 Section 6.4 Randomisation criteria	4
2.5 Section 8.6.2.1 Counselling in healthy nutrition.....	4

1 Introduction including rationale for the protocol amendment

The present local amendment for Mexico implements a requirement from the Research Committee to explicitly mention the ‘informed assent’ in the inclusion criterion number 1 to align with the text in protocol Sections 8.1.1 and 18.2.

In addition, editorial changes are addressed upon request from the Research Committee.

In this protocol amendment:

- Any new text is written *in italics*.
- Any text deleted from the protocol is written using ~~strike through~~.

2 Changes

2.1 Section 1.0 Summary

Trial design:

At least 30% of subjects will be from areas with lifestyle and nutrition comparable to ~~those subjects~~ in the European Union. All subjects will undergo counselling in healthy nutrition and physical activity for weight loss and must be prescribed a structured programme from the beginning of the 12-week run-in period and continuing through the 26-week follow-up period off trial drug.

Key inclusion criteria:

- Informed consent *from the legally acceptable representative (LAR) and informed assent from the subject* obtained before any trial-related activities. Trial-related activities are any procedures that are carried out as part of the trial, including activities to determine suitability for the trial.
- BMI corresponding to ~~$\geq 30 \text{ kg/m}^2$~~ $\geq 30 \text{ (kg/m}^2\text{)}$ for adults by international cut-off points and \geq the 95th percentile for age and sex (for diagnosis of obesity)

Key randomisation criteria:

- BMI corresponding to ~~$\geq 30 \text{ kg/m}^2$~~ $\geq 30 \text{ (kg/m}^2\text{)}$ for adults by international cut-off points and \geq the 95th percentile for age and sex (for diagnosis of obesity).

2.2 Section 5.1 Type of Trial

At least 30% of subjects will be from areas with lifestyle and nutrition comparable to ~~these subjects~~ in the European Union. All subjects will undergo counselling in healthy nutrition and physical activity for weight loss and must be prescribed a structured programme from the beginning of the 12-week run-in period and continuing through the 26-week follow-up period off trial drug. The trial design is shown schematically below:

2.3 Section 6.2 Inclusion criteria:

1. Informed consent *from the legally acceptable representative (LAR) and informed assent from the subject* obtained before any trial-related activities. Trial-related activities are any procedures that are carried out as part of the trial, including activities to determine suitability for the trial.
3. BMI corresponding to ~~$\geq 30 \text{ kg/m}^2$~~ $\geq 30 \text{ (kg/m}^2\text{)}$ for adults by international cut-off points and \geq the 95th percentile for age and sex (for diagnosis of obesity)

2.4 Section 6.4 Randomisation criteria

3. BMI corresponding to ~~$\geq 30 \text{ kg/m}^2$~~ $\geq 30 \text{ (kg/m}^2\text{)}$ for adults by international cut-off points and \geq the 95th percentile for age and sex (for diagnosis of obesity)

2.5 Section 8.6.2.1 Counselling in healthy nutrition

If a BMI corresponding to ~~$\leq 25 \text{ kg/m}^2$~~ $\leq 25 \text{ (kg/m}^2\text{)}$ for adults by international cut-off point⁵³ is reached, subjects should be assigned a maintenance diet, at the discretion of the investigator. For details, refer to Appendix A.

AD	available drop-out
ANOVA	analysis of variance
AT	available on treatment
BMI	body mass index
BMI SDS	body mass index standard deviation score
BOCF	baseline observation carried forward
CI	confidence interval
CRF	case report form
CTR	clinical trial report
CV	coefficient of variance
EoT	end-of-text
FAS	full analysis set
HbA1c	glycosylated haemoglobin
ISPAD	international society for pediatric and adolescent
LOCF	last observation carried forward
MD	missing drop-out
MedDRA	Medical Dictionary for Regulatory Activities
MT	missing on treatment
PD	pharmacodynamics
PK	pharmacokinetics
PP	per protocol
SAE	serious adverse event
SAP	statistical analysis plan
SAS	safety analysis set
SD	standard deviation
SE	standard error
LAR	legally acceptable representative

1 Introduction

1.1 Trial information

Trial design

This is a 56-week double-blind, randomised, parallel-group, placebo-controlled, multi-national trial followed by a 26-week period off study-drug. The trial will be conducted in pubertal adolescents with obesity aged 12 to less than 18 years. Subjects will be randomised 1:1 to receive liraglutide or placebo. The randomisation will be stratified according to pubertal and glycaemic status (see protocol Sections 5.2 and 11).

At least 30% of subjects will be from areas with lifestyle and nutrition comparable to those in the European Union. All subjects will undergo counselling in healthy nutrition and physical activity for weight loss and must be prescribed a structured programme from the beginning of the 12-week run-in period and continuing through the 26-week follow-up period off trial drug.

Primary objective

- To compare the efficacy of liraglutide versus placebo on weight loss in adolescent subjects with obesity after 56 weeks of treatment

Secondary objectives

- To compare the efficacy of liraglutide versus placebo on glycaemic control, cardiovascular risk factors and Impact of Weight on Quality of Life-Kids (IWQOL-Kids) in adolescent subjects with obesity after 30 and 56 weeks of treatment
- To compare the safety of liraglutide versus placebo in adolescent subjects with obesity after 30 and 56 weeks of treatment
- To examine the potential rebound effect from end of treatment at week 56 to week 82

Further details are described in the protocol section 4.2.

1.2 Scope of the statistical analysis plan

This SAP is based on the protocol “Effect of liraglutide for weight management in pubertal adolescent subjects with obesity”, version [final protocol version 1.0].

2 Statistical considerations

Results from the statistical analysis will generally be presented by two-sided confidence intervals (CIs) with a confidence level of 95%. Superiority will be claimed if the two-sided p-value is less than 5% and the treatment estimate favours liraglutide. If the upper limit is below 0, superiority of liraglutide against placebo can be concluded.

The full analysis set (FAS) will be used in the analysis of the efficacy endpoints. For the safety endpoints, the safety analysis set (SAS) will be used. The definition of the analysis sets is given section [2.1](#).

Laboratory values below the lower limit of quantification (LLOQ) will be set to $\frac{1}{2}$ LLOQ. The baseline value will be defined as the last measured and available value from randomisation (V9) and end of run-in (V8), if not otherwise specified.

2.1 Definitions of analysis sets

The following analysis sets are defined in accordance with the ICH E9^{1,2}.

- FAS: includes all randomised subjects who have received at least one dose of trial product and have any post-randomisation data. The statistical evaluation of the FAS will follow the intention-to-treat (ITT) principle and subjects will contribute to the evaluation “as randomised”.
- SAS: includes all subjects exposed to at least one dose of trial product. Subjects in the SAS will contribute to the evaluation “as treated”.

Before data are locked for statistical analysis, a blinded review of all data will take place. Any decision to exclude a subject or single observation from the statistical analysis is the joint responsibility of the Novo Nordisk trial statistician, the international trial manager and the international medical specialist. Exclusion of data from analyses will be used restrictively and normally no data should be excluded from the FAS. The subjects or observations to be excluded, and the reasons for their exclusion must be documented and signed by those responsible before database lock. The subjects and observations excluded from analysis sets, and the reason for this, will be described in the clinical trial report.

Any observation excluded from the analysis database will be documented before database lock with the reason for exclusion provided.

2.2 Primary endpoint

The primary endpoint is:

- Change from baseline in BMI SDS after 56 weeks of treatment.

The objective is to show that liraglutide is superior to placebo in obtaining weight loss. Let $\mu_{\text{liraglutide}}$ and μ_{placebo} denote the mean change in BMI SDS for liraglutide and placebo, respectively. The null hypothesis and the alternative hypothesis are:

$H_0: \mu_{\text{liraglutide}} = \mu_{\text{placebo}}$ against the alternative $H_A: \mu_{\text{liraglutide}} \neq \mu_{\text{placebo}}$

The null-hypothesis will be rejected on a 5% level if the two-sided 95% CI of the treatment FAS difference $\mu_{\text{liraglutide}} - \mu_{\text{placebo}}$ excludes 0. If the upper limit is below 0, superiority of liraglutide against placebo can be concluded.

The hypothesis will be tested using an analysis of covariance (ANCOVA) model using including the factors, covariates and interaction term listed in below table.

Table 2-1: Factors and covariates for the analysis of the primary endpoints

Factors and covariates at baseline	Type	Categories
Randomised treatment	Factors	Liraglutide 3.0 mg, Placebo
Sex	Factors	Female, Male
Region	Factors	Europe, North America
Glycaemic category	Factors	Yes, No*
Tanner stage, Glycaemic category	Interaction factor	Not applicable
Tanner stage	Factors	Stage 2 and 3 together, Stage 4 and 5 together
Baseline BMI SDS	Covariate	Not applicable
Age	Covariate	Not applicable

*Yes: dysglycaemic, No: non-dysglycaemic.

The factors and covariates will be included in the model as main effects in an additive structure. The estimated treatment difference between liraglutide 3.0 mg and placebo will be reported together with the associated two-sided 95% CI and corresponding p-value.

Missing data in the main analysis will be handled by the following multiple imputation (MI) method. A pattern mixture model approach is applied where withdrawn subjects or treatment discontinued subjects without a follow-up visit are assumed to respond as if treated with placebo for the entire trial. Multiple copies (100 copies) of the full dataset will be generated by imputing missing values based on estimated parameters for the placebo group. These missing data will be handled as mentioned in protocol section 17.3.

Table 2-2: Taxonomy of week 30, 56 and 82 assessments being available or missing

Assessment at week 30, 56 and 82	On randomised treatment at week 30, 56 and 82	Type description	Type abbreviation
Available	Yes	Available on randomised treatment: Subjects who did not discontinue randomised treatment prematurely.	AT
	No	Available drop-outs: Subjects who discontinued randomised treatment prematurely but returned to have an assessment at week 30, 56 and 82; so-called retrieved drop-outs.	AD
Missing	Yes	Missing on randomised treatment: Subjects who did not discontinue randomised treatment prematurely.	MT
	No	Missing drop-outs: Subjects who discontinued randomised treatment prematurely and did not return to have an assessment at week 30, 56 and 82; so-called non-retrieved drop-outs.	MD

2.2.1 Sensitivity analysis

To investigate the sensitivity of the results of the main analysis of the primary endpoint about the handling of missing data, a sensitivity analysis will be performed as mentioned below (further details refer protocol section 17.3).

- An ANCOVA will be performed with imputation of missing values according to the last observation carried forward (LOCF) method. The model will include terms for treatment, sex, region, baseline glycaemic category, stratification factor for Tanner stage and interaction between baseline glycaemic category and stratification factor for Tanner stage will be included as fixed effect and baseline BMI SDS and baseline age as covariates. The response variable will be the last available measurement of BMI SDS obtained within the 56-week double-blind period of the trial.
- The same type of ANCOVA as above will be performed but using an imputation of missing values according to the baseline observation carried forward (BOCF) method. Missing measurements of BMI SDS at 56 weeks will be imputed by the corresponding baseline values with this method.

- The same type of ANCOVA as above will be performed without imputation by only including subjects who completed the 56 weeks double-blind period.
- A mixed model for repeated measurements (MMRM) will be applied where all post baseline BMI SDS measurements obtained at planned visits during the 56-week double-blind period will enter as the dependent variables, and visit, treatment, sex, region, baseline glycaemic category, stratification factor for Tanner stage and interaction between baseline glycaemic category and stratification factor for Tanner stage will be included as fixed effects, and baseline BMI SDS and baseline age as covariates. All these factors and covariates will be nested under visit, which is technically the same as introducing the corresponding interaction terms in the model. An unstructured covariance matrix for the BMI SDS measurements within subject will be employed.

For further details refer protocol section 17.3.

2.3 Handling of missing values

2.3.1 Handling of missing values at baseline

If an assessment has been made both at screening and randomisation, the value from the randomisation visit will be used as the baseline value. If the value is missing at the randomisation visit and an assessment was available at screening, then the screening value will be used as the baseline value.

2.3.2 Handling of missing values at weeks 30, 56 and 82

Missing values at weeks 30, 56 and 82 will be imputed and the relevant endpoints will be analysed from the imputed values. Several approaches for imputation of missing values at weeks 30, 56 and 82 will be applied. First, a description of the primary imputation approach used to address the effectiveness for the primary endpoint is given. This is followed by a description of several sensitivity analyses.

Primary approach for handling missing values

The primary approach for multiple imputations of missing values of BMI SDS at week 30, 56 and 82 (type MT+MD [Table 2-2](#)) for both the liraglutide 3.0 mg and placebo group is by sampling all available assessments at respective landmark visits in the placebo group (type AT+AD). This approach is also known as jump to reference and makes the assumptions that subjects instantly after discontinuation lose any effect of randomised treatment beyond what can be expected from placebo treatment as adjunct to diet and exercise³. The multiple imputation approach is done in four steps.

Imputation: Step 1: 100 copies of the dataset will be generated.

Analysis: Step 2: Impute the missing value from placebo completers by fitting enriched regression model. Model will be fitted with the factors, covariates and interaction term in the same order as mentioned in [Table 2-3](#). The estimated parameters and their variances from this model were used to impute missing values at 56 weeks for subjects in both treatment arms, based on their factor levels and the values of the covariates.

Analysis: Step 3: For each of the 100 complete datasets, the change from baseline in BMI SDS at 56 weeks will be analysed using the main ANCOVA model with factors and covariates as mentioned in [Table 2-1](#).

Pooling: Step 4: Pool the 100 estimation results into a final result using Rubin's formula.

The imputation model in step 2 uses placebo subjects from FAS with non-missing BMI SDS at baseline and week 56. The imputation model is a linear regression of BMI SDS at week 56 on the factors and covariates listed in [Table 2-3](#) (except randomised treatment arm) with interaction term included in the model. The order of the factors and covariates has been retained as mentioned in [Table 2-3](#) while fitting imputation model. The estimated posterior distribution for the parameters (regression coefficients and variances) in the imputation model is then used to impute missing week 56 BMI SDS values for both randomised treatment arms.

Table 2-3: Factors and Covariate for imputation model

Factors and covariates at baseline	Type	Categories	Order
Sex	Factors	Female, Male	1
Region	Factors	Europe, North America	2
Baseline Glycaemic category	Factors	Yes, No	3
Tanner stage	Factors	Stage 2 and 3 together, Stage 4 and 5 together	4
Tanner stage, Glycaemic category	Interaction factor	Not applicable	5
Baseline BMI SDS	Covariate	Not applicable	6
Baseline Waist circumference	Covariate	Not applicable	7
Baseline Age	Covariate	Not applicable	8
Baseline HbA1c	Covariate	Not applicable	9

The multiple imputations will be generated using Novo Nordisk trial number 80224180 as seed number.

A similar procedure of imputation will be followed for all the secondary endpoints as mentioned in [Table 2-4](#) except while imputing missing values for waist circumference assessment, baseline waist circumference which will not be included in the imputation model. Similarly, for HbA_{1c} assessments, baseline HbA_{1c} will not be included in the imputation model.

For missing glycaemic category, the imputation will be done for missing FPG and HbA_{1c} assessments using the imputation model mentioned in [Table 2-4](#) except for HbA_{1c}, baseline HbA_{1c} which will not be used while imputing the missing values.

Table 2-4: Statistical analysis to address primary and secondary objectives

SI No.	Endpoints	Landmark visits	Endpoint type	Imputation approach and Statistical model	Analysis set	Sensitivity analyses
Primary Endpoint						
1	Change from baseline in BMI SDS	Week 56	Continuous	J2R-MI ANCOVA	FAS	
 • ANCOVA (LOCF) • ANCOVA (BOCF) • ANCOVA (no imputation, with 56 week completers) • MMRM
Secondary Endpoint						
2	Change from baseline in BMI SDS	Week 30, Week 82	Continuous	J2R-MI ANCOVA	FAS	NA
3	Change from baseline in BMI SDS (%)	Week 30, Week 56	Continuous	J2R-MI ANCOVA	FAS	NA
4	Change from baseline in BMI SDS	Week 56 to 82 (Week 56 as baseline)	Continuous	J2R-MI ANCOVA	FAS	NA
5	Change from baseline BMI	Week 30, Week 56	Continuous	J2R-MI ANCOVA	FAS	NA

	(Kg/m ²)					
6	Percentage of Subjects achieving $\geq 5\%$ reduction in baseline BMI	Week 30, Week 56, Week 82	Categorical	J2R-MI Logistic Regression	FAS	NA
7	Percentage of Subjects achieving $\geq 10\%$ reduction in baseline BMI	Week 30, Week 56, Week 82	Categorical	J2R-MI Logistic Regression	FAS	NA
8	Change from Baseline in PRO score (IWQoL)	Week 30, Week 56	Continuous	J2R-MI ANCOVA	FAS	NA
9	Change from baseline in Glycaemic category	Week 30, Week 56	Categorical	J2R-MI Logistic Regression	FAS	NA
10	Change from baseline in Body weight (kg and %)	Week 30, Week 56	Continuous	J2R-MI ANCOVA	FAS	NA
11	Change from baseline in Waist circumference (cm)	Week 30, Week 56	Continuous	J2R-MI ANCOVA	FAS	NA
12	Change from baseline in Waist-to-hip circumference ratio (ratio)	Week 30, Week 56	Continuous	J2R-MI ANCOVA	FAS	NA
13	Change from baseline Systolic Blood Pressure (mmHg)	Week 30, Week 56	Continuous	J2R-MI ANCOVA	FAS	NA
14	Change from	Week 30,	Continuous	J2R-MI	FAS	NA

	baseline Diastolic Blood Pressure (mmHg)	Week 56		ANCOVA		
15	Change from baseline Pulse (beats/min)	Week 30, Week 56	Continuous	J2R-MI ANCOVA	SAS	NA
16	Change from baseline in Cardiovascular biomarker (hsCRP) (mg/L)	Week 30, Week 56	Continuous	J2R-MI ANCOVA (with log transformed response and baseline values)	FAS	NA
17	Change from baseline in TC (mmol/L)	Week 30, Week 56	Continuous	J2R-MI ANCOVA (with log transformed response and baseline values)	FAS	NA
18	Change from baseline in LDL-cholesterol (mmol/L)	Week 30, Week 56	Continuous	J2R-MI ANCOVA (with log transformed response and baseline values)	FAS	NA
19	Change from baseline in HDL-cholesterol (mmol/L)	Week 30, Week 56	Continuous	J2R-MI ANCOVA (with log transformed response and baseline values)	FAS	NA
20	Change from baseline in non-HDL cholesterol (mmol/L)	Week 30, Week 56	Continuous	J2R-MI ANCOVA (with log transformed response and baseline values)	FAS	NA
21	Change from baseline in VLDL (mmol/L)	Week 30, Week 56	Continuous	J2R-MI ANCOVA (with log transformed response and baseline values)	FAS	NA
23	Change from baseline in TG (mmol/L)	Week 30, Week 56	Continuous	J2R-MI ANCOVA (with log transformed response and baseline values)	FAS	NA

24	Change from baseline in FFA (mmol/L)	Week 30, Week 56	Continuous	J2R-MI ANCOVA (with log transformed response and baseline values)	FAS	NA
25	Change from baseline in HbA1c (%)	Week 30, Week 56	Continuous	J2R-MI ANCOVA	FAS	NA
26	Change from baseline in FPG (mmol/L)	Week 30, Week 56	Continuous	J2R-MI ANCOVA	FAS	NA
27	Change from baseline in fasting insulin (pmol/L)	Week 30, Week 56	Continuous	J2R-MI ANCOVA (with log transformed response and baseline values)	FAS	NA
28	Change from baseline in fasting C-peptide (nmol/L)	Week 30, Week 56	Continuous	J2R-MI ANCOVA (with log transformed response and baseline values)	FAS	NA
29	Change from baseline in HOMA-B	Week 30, Week 56	Continuous	J2R-MI ANCOVA (with log transformed response and baseline values)	FAS	NA
30	Change from baseline in HOMA-IR	Week 30, Week 56	Continuous	J2R-MI ANCOVA (with log transformed response and baseline values)	FAS	NA

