6.4 Randomisation criteria

To be randomised, all randomisation criteria must be answered "yes".

1. BMI corresponding to ≥ 30 kg/m² for adults by international cut-off points and \geq the 95th percentile for age and sex (for diagnosis of obesity).
2. Compliance with run-in procedures and visit schedule as judged by the investigator.
3. PHQ-9 score < 15 at randomisation
4. No suicidal ideation of type 4 or 5 since last visit based on the C-SSRS questionnaire at randomisation

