8.1.4 Run-in visits

Subject's eligibility according to the in- and exclusion criteria must be evaluated before the 12-week run-in period is initiated.

V4 and V6 can be performed as phone visits. All subjects must be reminded to attend V8 and the randomisation visit in a fasting state.

During the run-in period the investigator should evaluate the subject's compliance with the run-in procedures and visit schedule. If deemed acceptable, as judged by the investigator, the subject can proceed to randomisation visit. If not, the subject is a screening failure ([8.1.5](#)).

All run-in assessments as described in Section [2](#) must be performed and data recorded in the eCRF. For screening failures, please refer to Section [8.1.5](#).

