8.3.1 Body measurements

8.3.1.1 Body weight

Body weight must be measured to the nearest 0.1 kg or 0.1 pounds. Fasting body weight must be measured at the fasting visits (Section [8.1.2](#)). If the weight is not measured fasting at fasting visits, the subject must be called in for a new visit within the visit window to have the fasting weight measured. At the remaining visits, the measurement is performed in a non-fasting state.

The same digital scale should be used throughout the trial. The scale must be calibrated according to the directions for use and, as a minimum, once a year.

Weight should be measured without shoes and only wearing light clothing and the subject should have an empty bladder.

Weight measured at screening is used for the calculation of BMI, whereas weight measured at randomisation is used as baseline for assessment of change in body weight. BMI is calculated in the eCRF.

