8.5.3 Laboratory assessments for efficacy

Any "abnormal, clinically significant" findings at screening must be recorded as medical history/concomitant illness in the eCRF. The following blood samples must be drawn (for frequency, see Section [2](#)):

Lipids (fasting):

- Total cholesterol
- LDL-cholesterol
- VLDL-cholesterol
- HDL-cholesterol
- Triglycerides
- FFA
- Non-HDL cholesterol (calculated value from central lab)

Biochemistry:

- hsCRP

Glucose metabolism (The measurement performed at V8 is considered baseline):

- HbA_{1c}
- FPG^a
- Fasting insulin
- Fasting C-peptide

HOMA-B and HOMA-IR will be calculated on glucose metabolism parameters to assess beta-cell function and insulin resistance.

^a**Fasting plasma glucose**

An FPG result ≤ 3.9 mmol/L (70 mg/dL) should not be reported as a hypoglycaemic episode but as a clinical laboratory adverse event (CLAE) at the discretion of the investigator; see Section [12.1.1](#).

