When visit windows are used, all visits will be re-aligned, i.e., they will be mapped into one of the visit windows. For example, if the Week 4 visit of a subject is delayed and occurs on Day 46 instead of on Day 29, it will be re-aligned to visit window Week 8. In the case of major deviations from the visit schedule, or due to unscheduled visits, several assessments of a subject may fall in a particular visit window (either scheduled or unscheduled). Statistical approaches to handle multiple assessments in a given visit window are specified below.

In general, if two consecutive visits V_t and V_s are x days apart, the upper limit of the visit window for V_t will be $V_t+x/2$ and the lower limit for the visit V_s will be $V_s-x/2$ (if x is even, the lower limit for V_s will be $V_s-x/2+1$, and the upper limit for V_t will be $V_t+x/2$). The algorithm needs to ensure that visit windows are not overlapping and that there are no gaps, such that each assessment can be uniquely allocated to one visit window, e.g., if Week 8 visit is scheduled for day 57, Week 12 is scheduled at Day 85 and Week 16 is scheduled at Day 113, then the visit window for week 12 extends from Day 72 to Day 99.

Note: The lower limit of first visit will be assigned with -999 which accommodate all assessments occurred before the scheduled day.

The upper limit of last visit will be assigned with 999 which accommodate all assessments occurred after the scheduled day.

Table 3-1: Assessment windows for scheduled visits

Analysis Visit	Week	Scheduled Day	Visit Window
Visit 2 (screening)	week -14	-98	Day -999 to -91
Visit 3 (week -12)	week -12	-84	Day -90 to -70
Visit 5 (week -8)	week -8	-56	Day -69 to -42
Visit 7 (week -4)	week -4	-28	Day -41 to -21
Visit 8 (week -2)	week -2	-14	Day -20 to -7
Visit 9 (week 0)	Randomisation	1	Day -6 to 4
Visit 10 (week 1)	week 1	8	Day 5 to 11
Visit 11 (week 2)	week 2	15	Day 12 to 18
Visit 12 (week 3)	week 3	22	Day 19 to 25
Visit 13 (week 4)	week 4	29	Day 26 to 43
Visit 14 (week 8)	week 8	57	Day 44 to 71
Visit 15 (week 12)	week 12	85	Day 72 to 99
Visit 16 (week 16)	week 16	113	Day 100 to 127
Visit 17 (week 20)	week 20	141	Day 128 to 158
Visit 18 (week 25)	week 25	176	Day 159 to 193
Visit 19 (week 30)	week 30	211	Day 194 to 225
Visit 19x (week 30 follow-up)	week 30	211	Day 194 to 225
Visit 20 (week 34)	week 34	239	Day 226 to 253
Visit 21 (week 38)	week 38	267	Day 254 to 281
Visit 22 (week 42)	week 42	295	Day 282 to 309

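### When the randomisation value is missing, SAP 2.3.1 falls back to the pre-run-in screening value and skips V8, in conflict with SAP 2 and protocol 17

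*SAP*

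**What the plan says.** The general rule stands in SAP 2 and, in the same words, in protocol 17: "The baseline value will be defined as the last measured and available value from randomisation (V9) and end of run-in (V8"), with a rider that leaves room for a different specification elsewhere. Under that rule a missing V9 value is replaced by V8.

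SAP 2.3.1 gives a second general rule. Where both a screening and a randomisation value exist, randomisation is used. Otherwise: "If the value is missing at the randomisation visit and an assessment was available at screening, then the screening value will be used" as baseline. V8 is not mentioned.

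Screening has a fixed place in the schedule. Protocol 8.1.3 is the section on the screening visit, visit 2. SAP Table 3-1 attaches the label only to the row that opens "Visit 2 (screening", at week -14.

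For one group of variables the protocol sets its own baseline. Of glucose metabolism (HbA1c, FPG, fasting insulin, fasting C-peptide), protocol 8.5.3 says: "The measurement performed at V8 is considered baseline". For ECG, protocol 8.4.4 names screening.

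SAP 3 lists the changes made to the analyses planned in the protocol. The rule for a missing V9 value is not among them.

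**The concern.** Two programmers, one working from SAP 2 and the other from SAP 2.3.1, would derive different baselines for the same subject. The SAP 2.3.1 value comes from before the run-in, during which every subject is counselled towards weight loss. Weight change in those 12 weeks would then be counted as change after randomisation.

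The baseline value is used widely. Baseline BMI SDS enters the primary change score, the ANCOVA, the imputation model and the BOCF analysis. Baseline BMI sets the 5% and 10% responder thresholds. Baseline HbA1c is a covariate in the imputation model (SAP Table 2-3), so an unclear glucose baseline also reaches the primary analysis.

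**Working it through.** **1. Is a V8 value planned for the primary variable?** Protocol 8.1.4: "All subjects must be reminded to attend V8 and the randomisation visit in a fasting state". Protocol 8.3.1.1: "Fasting body weight must be measured at the fasting visits". So weight is due at V8. SAP Table 3-2 lists V8 as a height visit (window day -55 to -7). Weight and height together give BMI and BMI SDS at V8.

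**2. The two rules applied to each pattern of available values**

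| V9 | V8 | V2 | SAP 2 / protocol 17 | SAP 2.3.1 |
|---|---|---|---|---|
| present | present | present | V9 | V9 |
| missing | present | present | V8 | V2 |
| missing | missing | present | none | V2 |
| missing | present | missing | V8 | not triggered |

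The second row is the conflict. In the third row SAP 2.3.1 only adds a last resort, which is harmless.

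**3. Age of the value.** SAP Table 3-1 gives V2 at day -98, V3 (start of run-in) at day -84 and V8 at day -14. V2 is 98 - 14 = 84 days older than V8, and 98 - 84 = 14 days before run-in starts.

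**4. Size.** The documents give neither the share of subjects without a V9 BMI nor the change in BMI during run-in. Assumed: share f = 1-5% (2 to 11 of 228) and a fall r = 1-3% in BMI. A gain would reverse the signs.

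- Affected subject with BMI 30 kg/m2: 30 x 0.01 = 0.30 to 30 x 0.03 = 0.90 kg/m2 of run-in change is counted as treatment-period change.
- In BMI SDS, using the SAP 2.5.1 worked example (28.03 - 22.45 = 5.58 kg/m2 per SDS above +3 SD): 0.30/5.58 = 0.054 to 0.90/5.58 = 0.161. The example is an 11-year-old boy, outside the trial's age range, so this is illustration only.
- Further loss needed to count as a 5% responder: 1 - 0.95/(1 - r) = 4.04% at r = 1% and 2.06% at r = 3%. For 10%: 1 - 0.90/(1 - r) = 9.09% and 7.22%.
- Shift in an arm's mean BMI change, f x r: 0.01 x 1% = 0.01 to 0.05 x 3% = 0.15 percentage points. In BMI SDS: 0.01 x 0.054 = 0.0005 to 0.05 x 0.161 = 0.008.

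**5. Effect on the primary test** (normal approximation, unadjusted, protocol 17.1 inputs). With 114 per arm and 40% withdrawal, the expected difference is 0.6 x 0.26 = 0.156. The variances are 0.35² = 0.1225 on placebo and 0.1225 + 0.4 x 0.6 x 0.26² = 0.1387 on liraglutide. SE = √((0.1225 + 0.1387)/114) = 0.0479 and power is 0.903, in line with the protocol's 90% for 228 subjects.

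Let m and s be the assumed mean and SD of run-in SDS change. Each arm's variance then rises by f·s² + f(1 - f)·m².

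- f = 1%, m = 0.05, s = 0.10: power 0.903.
- f = 5%, m = 0.16, s = 0.20: each variance rises by 0.0020 + 0.0012 = 0.0032, SE = 0.0485, power 0.896.

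The run-in precedes randomisation, so the expected shift is the same in both arms and the difference stays at 0.156.

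**6. Glucose metabolism.** SAP 2.3.1 read literally, against V8 in protocol 8.5.3:

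- measured at V2 and V9: gives V9;
- measured at V2 but not V9: gives V2;
- measured at neither: not triggered, and SAP 2 still returns V8.

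Which case applies depends on the laboratory rows of the protocol flowchart. Those rows are not in the text available for this review, so no count or size is given.

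**The case against.** The best defence is that SAP 2.3.1 is headed as a rule for missing baselines, and under SAP 2 a baseline is missing only if both V9 and V8 are. It would then simply add a last resort. That is a sensible intention, but the trigger is worded as a value missing at the randomisation visit, and V8 is not mentioned.

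A second defence is the rider in SAP 2 that permits other specifications. SAP 2.3.1 applies to all variables, however. If it were the exception, V8 would be used only when V9 and screening were both absent, and the V8 clause would be almost empty. It would also be a change from protocol 17 that SAP 3 does not declare.

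Third, screening could be meant loosely: protocol 17.4.1.2 uses the term for the time before randomisation. Visit 2 remains the natural reading, and the loose one leaves open which value to take. Protocol 8.3.1.1 does calculate BMI from screening weight, but for change in weight it says "weight measured at randomisation is used as baseline for assessment of change in body weight", and the primary endpoint takes randomisation as baseline.

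What stands is that the trigger should be rare for BMI. "To be randomised, all randomisation criteria must be answered" affirmatively, and the first of them is the BMI criterion. The sizes above also rest on assumptions. For waist circumference, lipids and IWQOL-Kids a V8 value cannot be confirmed; where there is none, a screening fallback conflicts with nothing.

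**Conclusion.** The conflict is real and should be corrected, as a minor point. As written, SAP 2.3.1 can select a pre-run-in baseline when a later V8 value exists. For an affected subject this changes the change score and can change responder status. Across an arm the shift is at most 0.15 percentage points of BMI or 0.008 BMI SDS, and power is at least 0.896 against 0.903, all under the assumed 1-5% share and 1-3% run-in fall. No between-arm bias is expected and the effect on the primary test is negligible.

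A reader might infer more in two ways. One is to set the 0.05-0.16 SDS shift against the planned difference of 0.26 and call the effect large. That compares one subject's shift with a difference in group means, so it says nothing about the treatment estimate. The other is to conclude that all glucose baselines are wrong. That would follow only if glucose was measured at V2 or V9, which could not be established. What the documents support is that SAP 2.3.1 states no exception for the V8 glucose baseline.

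**What to change.** Replace SAP 2.3.1 with a single hierarchy: V9; if missing, V8; screening only if both are missing. Restate beside it the protocol's own exceptions: V8 for glucose metabolism (protocol 8.5.3) and screening for ECG (protocol 8.4.4). Report the number of subjects by baseline source for each endpoint.

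The cost is a few sentences in the SAP, the matching derivation in the analysis programs and one count table. No new data or visits are needed, and because screening stays as the last resort, no subject loses a baseline.
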